#### H. Sample Size Considerations

The sample size consideration was based on the test for the primary hypothesis that patients who received Naloxegol 25 mg given once in the morning every day will have lower volume of residual urine in bladder when compared to placebo. We would need 62 patients per group [56] to have 90% power at a 2-sided alpha level of 0.05 to detect an effect size of 0.4 or more. The effect size estimation of 0.4 was very conservative as compared to the mean difference of 120 ml (SD: approximate 60 ml) in the volume of residual urine observed by Jose Carlos, I. T., et al [57]. The effect size is the difference in means of the two randomized groups divided by the pooled standard deviation. A maximum of six measurements are planned, twice per day for 3 days. However, we assumed 4 measurements per patients with a correlation of 0.3 to be conservative for the sample size calculation. Considering a loss of follow-up rate of 10%, we will need 12 more patients to reach the planned power with an end sample size of 136. A blinded data quality check will be conducted at 50% (68 patients) of the planned enrollment of 136 patients. In addition to the 136 patients, we will enroll 2 pilot patients to test feasibility of recruitment, protocol adherence, randomization process, and data collection.

SAS software version 9.4 for Windows (SAS Institute, Cary, NC) will be used for all statistical analyses and graphics.

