#### 2. STUDY DESIGN and METHODS

#### A. Study Overview

We propose to assess the effect of Naloxegol on reversing opioid-related side effects in patients recovering from elective primary hip surgery under spinal anesthesia who will be randomly assigned to oral Naloxegol or placebo for two postoperative days or until the date of discharge, whichever occurs earlier (**Table 1**). The design will be a randomized, double-blind, placebo-controlled trial of oral Naloxegol in adults having elective primary hip or knee surgery under spinal anesthesia. The study will be performed at the Cleveland Clinic hospitals.

	Preopera tive visit	Morning of surgery	During surgery	PACU*	POD** 1	POD 2	Day of discharge	
Screening for eligibility	Х	Х						
Consenting	Х							
Baseline medical, demographics, Apfel score, Patient functionality and drug history	Х	х						
Pertinent blood studies (laboratory)	Х				Х	х		
AE/SAE collection		Х			Х	Х		
Study drug (in morning, 1 hr before or 2 hr after meal)		Х			х	х		
Bladder scan at least 2 hours after study drug (morning)					х	Х		
Bladder scan (evening)				Х	х	Х		
Intraoperative record data collection			Х					
Opioid–Related Symptom Distress Scale (ORSDS)					х	х	Х	
Opioid complications survey***				X	х	Х	х	
Numerical pain score				Х	Х	Х	Х	Х
Quality of recovery survey							Х	

Table 1: study flowchart.(Detailed information will be in the CRF's)

\* PACU = post-anesthesia care unit

\*\* POD = post-operative day

\*\*\* Opioid complications survey includes nausea, vomiting, itching, ileus, anti-emetic use, antipruritic use, anti-opioid use

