In the PACU and postoperative periods, patients will be managed at the discretion of the primary care team and the staff anesthesiologist. The need for straight catheterization in PACU and/or on the floor when it is medically indicated (volumes exceeding 400 ml) will be recorded by the study team and subsequent bladder scan will therefore not be done. Postoperatively, all patients will be given intravenous or oral opioids for pain control. Clinicians will adjust analgesic management as necessary in an effort to adjust verbal response pain scores to less than 4.

Clinical evaluators for the outcomes will be blinded to group allocation and Pharmacy personnel not involved in evaluations will prepare the study drugs. Clinicians including nurses will be blinded to monitoring and will be required to perform their standard of care management after surgery.

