#### **Enrollment procedures**

The following events will occur in order:

- 1. Screening for eligible patients
- 2. Informed consent
- 3. Randomization

- 4. Administration of study drug starting the morning of surgery and for 2 additional mornings
- 5. Collection of data
- 6. Completion of CRF information

The treatment periods extends from the morning of surgery until the earlier of POD 2 or hospital discharge. Study personnel will follow the study subject until the earlier of POD 2 or hospital discharge. In the case of an adverse event, the study subject will be followed until the resolution of the event.

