#### Primary analysis.

We will test the primary hypothesis that subjects who received Naloxegol 25 mg given once in the morning every day will have lower volume of residual urine in bladder when compared to placebo. We will compare the randomized groups on the volume of residual urine in bladder, which will be measured twice per day for up to 3 days (i.e., a maximum of 6 measurement times in total), using a linear mixed model adjusting for the within-subject correlation (using an autoregressive correlation structure). At each measurement time, the average of the measurements will be analyzed. Any imbalanced baseline characteristics and volume of residual urine in bladder prior to the procedure will be included as covariates in the model. If the group-by-time interaction is non-significant (P > 0.20), we will assess the group difference on the volume of residual urine across over all the measurements. In the presence of a group-by-time interaction, the group difference will be assessed separately at each measurement time and a Bonferroni correction will be made for multiple comparisons to maintain the hypothesis-wise 2-sided type I error at 0.05 (the significance criterion will be 0.05 / 6).

Second, we will assess the treatment effect within chronic opioid users and nonusers using the same statistical methods as above. The significance level will be 0.025 for each of the two subgroup analyses (Bonferroni correction).

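### The 90% power assumes 4 scans at correlation 0.3 and calls this conservative, but Table 1 allows at most 5 scans, not six, and a low correlation is the favourable direction

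*Combined protocol and SAP*

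**What the plan says.** Section H (Sample Size Considerations) states: "We would need 62 patients per group [56] to have 90% power at a 2-sided alpha level of 0.05 to detect an effect size of" (the value given is 0.4). It defines the scale: "The effect size is the difference in means of the two randomized groups divided by the pooled standard deviation". On the repeated scans it says "A maximum of six measurements are planned, twice per day for 3 days", and then that "we assumed 4 measurements per patients with a correlation of 0.3 to be conservative for the sample size calculation". It gives no source or range for the correlation.

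The primary analysis in Section G repeats the count. Residual volume is "measured twice per day for up to 3 days (i.e., a maximum of 6 measurement times in total"). The model is a linear mixed model with an autoregressive structure. Groups are compared over all measurements unless there is a group-by-time interaction, in which case each time is tested at 0.05/6.

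Table 1 in Section A (Study Overview) shows a different schedule. The morning row is marked on POD 1 and POD 2. The row "Bladder scan (evening)" is marked under PACU, POD 1 and POD 2. Section F describes the twice-daily procedures as done on the ward.

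Two provisions can reduce the number of scans. Under Enrollment procedures, "Study personnel will follow the study subject until the earlier of POD 2 or hospital discharge". In Section E, once straight catheterisation has been needed, "subsequent bladder scan will therefore not be done".

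**The concern.** Four scans look cautious beside six. Beside Table 1 they do not: four is the maximum, or one below it, before any patient goes home early or is catheterised. The correlation also works in the trial's favour. When groups are compared over all of a patient's scans, each further scan adds less information the more the scans resemble one another, so a value of 0.3 gives more power than a higher one.

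The stated power depends heavily on these two inputs. With one scan per patient, 90% power at effect size 0.4 would need 132 per group. About half of that is saved by assuming 4 scans at 0.3. A reader told that the inputs are conservative will take 90% as a floor, and the documents do not establish that it is one.

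**Working it through.** **Inputs.** From Section H: 62 per group, effect size d = 0.4 (so SD = 1), two-sided alpha 0.05, power 90%, m = 4 scans, correlation ρ = 0.3. From Section E: 1:1 allocation. From Table 1: the scan schedule. Not in the documents, and so varied here: the number of scans actually obtained and the true correlation.

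**Step 1: count the scans.** Table 1 gives 2 morning + 3 evening = 5, or 2 + 2 = 4 if the surgery-day PACU scan is not done. Twice daily for 3 days would be 2 × 3 = 6. The missing sixth scan would be a morning scan on the day of surgery, which Table 1 does not schedule. The residual volume before the procedure, named in Section G, is a covariate and not an outcome scan.

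**Step 2: reproduce the 62.** For the mean of m equally correlated scans, the variance factor is f = (1 + (m − 1)ρ)/m.
- f = (1 + 3 × 0.3)/4 = 0.475.
- n per group = 2 × ((1.960 + 1.282)/0.4)² × f = 131.34 × 0.475 = 62.4.
- Power at 62 = Φ(0.4 × √(62/(2 × 0.475)) − 1.96) = Φ(1.27) = 89.8%.

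The stated figure is therefore reproduced with equal correlation between all pairs of scans.

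**Step 3: vary the inputs at 62 per group.** Under a first-order autoregressive structure (scans treated as equally spaced) the factor is f = 1/(1′V⁻¹1), which for m = 4 and lag-1 0.3 is 0.382. The power formula is unchanged.

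| Scans | Equal, 0.3 | Equal, 0.5 | Lag-1, 0.3 | Lag-1, 0.5 |
|---|---|---|---|---|
| 5 | 91.9% | 82.0% | 97.7% | 92.5% |
| 4 | 89.8% | 80.4% | 95.0% | 88.3% |
| 3 | 86.2% | 77.9% | 89.4% | 82.0% |
| 2 | 78.9% | 73.0% | 78.9% | 73.0% |

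Six scans at equal correlation 0.3 would give 93.2%, so 4 is cautious relative to six. Lag-1 0.3 with 4 scans would need only 51 per group, so the 62 does not match the autoregressive reading.

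**Step 4: mixed scan counts.** Averaging the information 1/f over patients at equal correlation 0.3, half with 4 scans and half with 2 gives 85.2%. Half with 5 and half with 3 gives 89.4%.

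**The case against.** Several points on the other side stand.

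- A reader might infer that 90% power holds only if practically every patient stays to POD 2, is never catheterised and gives about 4 scans. The documents do not support that. If the PACU scan is done, a patient can miss one scan and still give 4, and an even mix of 5 and 3 scans gives 89.4%. Under the lag-1 reading, 3 scans from every patient still give 89.4%.
- The planned model is autoregressive. If 0.3 is a lag-1 value, the losses are smaller, although the direction is the same and 2 scans still give 78.9%.
- The word conservative may have been meant for the count alone, as a contrast with six. The sentence can be read either way, but it attaches the word to both inputs and nothing else supports the 0.3.
- The catheterisation sentence may mean that only the next scan is skipped. How many scans would be lost is unknown.
- Table 1 was recovered from a PDF and its columns are irregular. The count uses the number of marks in each row, which does not depend on column alignment, but it should be checked against the source table. The Version 4 change log mentions removing the surgery-evening requirement. That log describes superseded text, so the choice between 4 and 5 is left open here.
- Section H sets 0.4 against a cited difference of 120 ml with SD about 60 ml, a ratio of 2.0. Even with 2 scans at equal correlation 0.6 (f = 0.8), 62 per group has 90% power for an effect of 0.52. This is a real margin on effect size, but a separate one. It does not make the scan count or the correlation conservative for the power claimed at 0.4.

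**Conclusion.** The stated maximum of six does not agree with Table 1, and the conservative label is unsupported for both inputs. Against the schedule, 4 scans is the maximum or one below it, and 0.3 lies on the favourable side of any higher correlation. If 3 or 2 scans are obtained at equal correlation 0.3, power falls from 89.8% to 86.2% or 78.9%. With 4 scans at 0.5 it is 80.4%, or 88.3% if 0.5 is a lag-1 value.

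A reader might go further and conclude that the trial is underpowered. The documents do not show this. They give no length of stay, catheterisation rate or observed correlation, and some admissible combinations exceed 90% (5 scans at equal correlation 0.3: 91.9%; 4 scans at lag-1 0.3: 95.0%). The fault is an unsupported label and a missing sensitivity range, not a demonstrated shortfall.

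**What to change.** 1. Reconcile the number of scans across Table 1, the primary analysis in Section G and Section H, and say whether the surgery-day PACU scan is an outcome scan.
2. Carry that number into the by-time criterion, which should divide by the actual number of post-treatment measurement times: 0.05/5 = 0.01 or 0.05/4 = 0.0125, against 0.05/6 ≈ 0.0083 now. Changing Section H alone would leave Section G in conflict with it.
3. In Section H, remove the claim of conservatism and state whether 0.3 is a common correlation or a lag-1 value.
4. Restate power as a range over 2 to 5 scans and plausible correlations, as in the table above.
5. At the blinded check already planned at 68 patients, summarise scans per patient and the within-patient correlation, pooled over arms.

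The cost is some rewording and one blinded summary. The stated power becomes less favourable. No added patients are required and no allocation is revealed.

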#### I. Blinding and unblinding

Study drug will be prepared by the hospital pharmacy and labeled as "Naloxegol 25 mg or Placebo". Placebo will have an identical shape and color. Blinding will be maintained unless unblinding is requested for an adverse event or any other reason as deemed necessary.

If clinically indicated, an investigator can request unblinding for a specific dose from the Pharmacy personnel. Such an event will be reported and documented. Unblinding can also be requested by the data safety and monitoring board at any time for safety concerns.

#### J. Treatment compliance

Subjects will be given clear instructions on medication doses and research-related follow-up prior to enrollment. A member of the study team will follow each patient for the duration of the intervention in order to ensure compliance with the protocol. Any deviations will be reported on the case report form and communicated as necessary.

If the need arises to discontinue the investigational product, the investigator will inform Pharmacy personnel to halt any further drug dispensing. The team will also communicate with the primary care nursing staff to return any unused investigational drug to the pharmacy for proper disposal.

#### 4. Safety monitoring and reporting

#### **Definition of adverse events**

An adverse event is the development of an undesirable medical condition or the deterioration of a pre-existing medical condition following or during exposure to a pharmaceutical product, whether or not considered causally related to the product. An undesirable medical condition can be symptoms (eg, nausea, chest pain), signs (eg, tachycardia, enlarged liver) or the abnormal results of an investigation (eg, laboratory findings, electrocardiogram). In clinical studies, an AE can include an undesirable medical condition occurring at any time, including run-in or washout periods, even if no study treatment has been administered.

The term AE is used to include both serious and non-serious AEs.

Adverse events of particular interest are:

Opioid withdrawal: hyperhidrosis, chills, diarrhea, abdominal pain, anxiety, irritability

Severe abdominal pain (>8/10) and/or diarrhea

Gastrointestinal perforation

## Definitions of serious adverse event

A serious adverse event is an AE occurring during any study phase that fulfills one or more of the following criteria:

Results in death

Is immediately life-threatening

Requires in-patient hospitalization or prolongation of existing hospitalization

Results in persistent or significant disability/incapacity or substantial disruption of the ability to conduct normal life functions

Is a congenital abnormality or birth defect

Is an important medical event that may jeopardize the subject or may require medical intervention to prevent one of the outcomes listed above.

The causality of SAEs (their relationship to all study treatment/procedures) will be assessed by the investigator(s) and communicated to AstraZeneca.

## **Causality assessment**

The Investigator will assess causal relationship between Investigational Product and each Adverse Event, and answer 'yes' or 'no' to the question 'Do you consider that there is a reasonable possibility that the event may have been caused by the investigational product?'

For SAEs a causal relationship will also be assessed for other concomitant medications, study procedures, and comparator study drugs. Note that for SAEs that could be associated with any study procedure the causal relationship is implied as 'yes'.

## Time period for collection of adverse events

Patients enrolled in the study will be followed until discharge from hospital. Adverse events occurring during this period will be recorded and communicated to the principal investigator and study team. Any events deemed serious by the principal investigator will be communicated to the IRB and Astra Zeneca as required and within 10 days of discovering the event.

## Follow-up of unresolved adverse events

The principal investigator and the study team will follow any unresolved adverse events and communicate with the IRB and Astra Zeneca accordingly.

The following variables will be collected for each AE:

AE (verbatim)

The date when the AE started and stopped

Whether the AE is serious or not

Investigator causality rating against the Investigational Product (yes or no)

Action taken with regard to investigational product

AE caused subject's withdrawal from study (yes or no)

Outcome of AE(s)

In addition to the AE variables referenced above, the following variables will be collected for SAEs:

Date AE met seriousness criteria

Date Investigator became aware of serious AE

AE is serious due to which criterion

If hospitalization or prolongation of hospitalization:

Date of hospitalization

Date of discharge If death: Probable cause of death Date of death Autopsy performed (Yes/no) and conclusion of cause of death from autopsy Causality assessment in relation to Study procedure(s) Causality assessment in relation to Other medication

## **Description of AE(s)**

An AE of severe intensity need not necessarily be considered serious. For example, nausea that persists for several hours may be considered severe nausea, but not a SAE. On the other hand, a stroke that results in only a limited degree of disability may be considered a mild stroke but would be a SAE.

## Adverse Events based on signs and symptoms

When collecting AEs, the recording of diagnoses is preferred (when possible) to recording a list of signs and symptoms. However, if a diagnosis is known and there are other signs or symptoms that are not generally part of the diagnosis, the diagnosis and each sign or symptom will be recorded separately.

## Adverse Events based on examinations and tests

Deterioration as compared to baseline in protocol-mandated laboratory values and/or vital signs should only be reported as AEs if they fulfill any of the SAE criteria or are the reason for discontinuation of treatment with the investigational product.

If deterioration in a laboratory value/vital sign is associated with clinical signs and symptoms, the sign or symptom will be reported as an AE and the associated laboratory result/vital sign will be considered as additional information. Wherever possible the reporting investigator uses the clinical, rather than the laboratory term (eg, anemia versus low hemoglobin value). In the absence of clinical signs or symptoms, clinically relevant deteriorations in non-mandated parameters should be reported as AE(s).

Deterioration of a laboratory value, which is unequivocally due to disease progression, should not be reported as an AE/SAE.

Any new or aggravated clinically relevant abnormal medical finding at a physical examination as compared with the baseline assessment will be reported as an AE.

## **Disease progression**

Disease progression can be considered as a worsening of a subject's condition attributable to the disease for which the investigational product is being studied. It may be an increase in the severity of the disease under study and/or increases in the symptoms of the disease. Events, which are unequivocally due to disease progression, should not be reported as an AE during the study.

## Overdose

Overdose in itself is not considered to be an AE or SAE.

Investigator/site staff are responsible for recording and reporting overdose in accordance with the clinical study protocol instructions. All overdoses with AstraZeneca product are collected and reported to AstraZeneca. Overdoses associated with SAEs will be reported according to SAE reporting. All other overdoses can be sent to AstraZeneca on a monthly basis.

The following information should be provided in the event of an Overdose (Overdose Report Form can be provided upon request):

Details of the Patient who was dispensed study medication (Randomization code)

Details of the Patient who took the overdose (demographic information, was patient a study participant?)

Details of the drug overdose (total daily dose, route, formulation, Overdose start and stop dates)

Was the overdose accidental or intentional?

Was the overdose associated with an adverse event (serious or non-serious)

Provide an Adverse Event description (use same wording as in CRF). Provide start and stop dates of the event, or indicate if the event is ongoing.

Provide Investigator's signature and date.

## Pregnancy

Pregnancy in itself is not considered to be an AE or SAE. However, if the subjects become pregnant during the study, Investigator/site staff are responsible for recording and reporting pregnancies and their pregnancy outcomes until pregnancy resolution in accordance with the clinical study protocol instructions.

If a patient becomes pregnant during the course of the study the study medication should be discontinued immediately. The investigator must inform AstraZeneca of any pregnancies occurring in a female patient or a female partner of a male patient within 24 hours of when he or she becomes aware of it.

## Maternal exposure

All reports of pregnancy with an AstraZeneca product (that is, those with or without associated SAE, AE or no symptoms) are collected and reported to AstraZeneca. If the pregnancy is accompanied by an SAEs (e.g. events of congenital abnormality/birth defect, spontaneous miscarriage or ectopic pregnancy, or any complications in the subject which meet the criteria for a serious adverse event), it should be reported according to the SAE reporting requirement. All other maternal exposure reports can be sent to AstraZeneca on a monthly basis.

Normal births and elective abortions without complications are not considered to be SAEs.

## **Paternal exposure**

If paternal exposure pregnancy occurs in the course of the study, then the Sponsor/Investigators should inform AstraZeneca within the same timeframe as the maternal exposure. The female partner of the patient will be asked to consent to allow collection of information and follow-up on the pregnancy. The outcome of the pregnancy is also followed and reported in accordance with the processes written in maternal exposure section.

